### ***7.3. Subject Status and Classification***

All enrolled subjects will be classified into one of three categories based on their progress and completion of key events. Classification will determine how data gathered from them will be stored and evaluated.

- **INTENT**: Any subject that signs the consent form but does not have any study devices inserted into the body. Subjects who are enrolled in the study but do not undergo ablation procedure within 60 days from consent signature date may not be reconsented and will be withdrawn from the study and classified as “INTENT”. INTENT subjects will count towards the enrollment ceiling and will not be used for analysis of the endpoints. INTENT subjects will not be followed for any additional visits after withdrawal. For these subjects an “End of Study” form must be completed. The original signed Informed Consent must be maintained in the center’s subject file.
- **ATTEMPT**: Any subject that signs the consent form, meets eligibility criteria and has any protocol defined study device inserted into the body but does not receive RF ablation per protocol. Additionally, any subject not treated with a BSC OI Catheter **and** the Rhythmia System will be considered an ATTEMPT. Use of the IntellaMap Orion Catheter is required but will not affect subject classification. Procedures that do not utilize the IntellaMap Orion Catheter will have a protocol deviation entered. Subjects will be followed for one month for safety reporting only. Therefore, ATTEMPT subjects will not be assigned an event monitor for study purposes. All applicable case report forms must be completed, including Baseline, data pertaining to the Index

procedure, Adverse Event reporting and one-month follow-up. ATTEMPT subjects will count towards the enrollment ceiling and will not be used for analyses of the primary endpoint. The original signed Informed Consent must be maintained in the center's study file.

- **TREATMENT:** Any subject that signs the consent form, meets eligibility criteria and has the specified study devices inserted into the body and undergoes protocol specific treatment for the intended disease.

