### ***3.3. IntellaMap Orion High Resolution Mapping Catheter***

The IntellaMap Orion High Resolution Mapping Catheter is an 8.5F, 115 cm working length, 64-electrode steerable catheter. The basket-shaped distal region consists of eight splines that comprise the electrode array. The proximal end has a handle that extends to a cable with a connector. The handle includes bi-directional articulation controls and a deployment slider that activates the electrode array into a basket shape once inside the heart. A flushing port extends from the back of the connector for connection to a continuous pressurized saline drip. The catheter is supplied with an 8.5F insertion sleeve for insertion through the hemostasis valve of an introducer sheath. A sensor in the catheter tip enables the position of the distal region of the catheter to be tracked in space when used with the Rhythmia™ Mapping System. Subsequent versions of the IntellaMap Orion mapping catheter may be used during this study as they become commercially available after regulatory approval in their geography.

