## 17. Committees

### 17.1. *Safety Monitoring Process*

Clinical Sites will report all study device related AEs, study procedure related AEs, and serious AEs to the sponsor as assessed by the clinical investigator. Investigators will be tasked to determine whether a subject has experienced one of the events specified in Section 4.1, counting towards the primary safety endpoint.

Since device and procedure relatedness do not affect the study endpoints, an independent CEC is not necessary to eliminate bias. The determination of relatedness is used for BSC safety assessment, but not in determining endpoint events. NOTE: The primary safety endpoint includes all deaths within 7 days or pre-discharge (whichever is later) regardless of relatedness to study device or procedure.

All reported adverse events will be reviewed on a regular basis by BSC's Medical Safety Group and study team to evaluate subject safety. The BSC Medical Safety group includes physicians with expertise in Electrophysiology and with the necessary therapeutic and subject matter expertise to evaluate and classify the events. During scheduled monitoring activities, clinical research monitors will support this continuous review through their review of source document and other data information.

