3.4 Tertiary endpoint

Chronic Effectiveness: Evaluation of chronic recurrence at 24 months and 36 months

- Recurrence is defined as intervention for atrial fibrillation, or new onset of atrial flutter or atrial tachycardia (repeat procedures, use of AADs, cardioversion), excluding repeat procedures during the 90-day blanking period.
- Data collection to include the diagnostic modality used to identify recurrence and the therapeutic intervention
- Chronic effectiveness will be evaluated using Kaplan-Meier methodology. The Kaplan-Meier 24 month and 36 month chronic recurrence-free rate will be calculated and presented along with the 95% confidence interval, calculated as the pointwise confidence limit using the log-log methodology. Subjects who die or withdraw from the study prior to the specified time point without experiencing an event will be censored on the date of death or on the date of withdrawal.

Center Experience: Primary safety and Primary effectiveness outcomes by center experience

- In order to evaluate training effectiveness for investigators outside of the ZERO AF IDE study, outcomes in centers performing five or more procedures using the Blazer OI catheter during the ZERO AF IDE study will be compared to all other. Kaplan-Meier rates and 95% confidence intervals for the Primary Safety and Effectiveness endpoints for both groups will be presented with no statistical comparison.

Safety: Reportable Adverse Events rates at 12, 24 and 36 months

Adverse events will be collected at all subject follow-up visits. Reportable events include:

- All Serious Adverse Events
- All Study Procedure-Related Adverse Events
- All Study Device-Related Adverse Events
- All Study Device Deficiencies
- Unanticipated Adverse Device Effects/Unanticipated Serious Adverse Device Effects previously not defined in the Directions For Use.

Adverse event rates will be calculated using binomial methodology. The cumulative number of events and event rate will be included in all study reports. Subjects at risk for an adverse event will be determined by the subject treatment status; all treatment and attempt subjects will be considered at risk for study related adverse events

Effectiveness: Acute Procedural Success Rate

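### A harm that stops the procedure before a study device enters leaves the primary safety test, and the protocol and SAP define the primary safety set in two ways

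*Protocol*

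**What the plan says.** Protocol 7.3 sorts enrolled subjects into three classes.

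- **INTENT** is "Any subject that signs the consent form but does not have any study devices inserted into the body". On use in the analysis: "INTENT subjects will count towards the enrollment ceiling and will not be used for analysis of the endpoints". On follow-up: "INTENT subjects will not be followed for any additional visits after withdrawal".
- **ATTEMPT** is an eligible, consented subject who "has any protocol defined study device inserted into the body but does not receive RF ablation per protocol". A second sentence begins "Additionally, any subject not treated with a BSC OI Catheter" and, adding the Rhythmia System as a joint condition, makes such a subject an ATTEMPT too. ATTEMPT subjects have one month of safety follow-up, and 7.3 keeps them out of the primary endpoint analyses.
- **TREATMENT** is a subject in whom the study devices are inserted and who undergoes the protocol treatment.

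The study devices (Protocol synopsis, SAP 1.2) are the open-irrigated ablation catheters, the Rhythmia system and the Orion catheter. No sheath, needle or anesthesia equipment is listed. Protocol 3.3 describes a sleeve supplied with the Orion catheter "for insertion through the hemostasis valve of an introducer sheath", so venous access comes before that catheter.

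The acute part of the primary safety composite (Protocol 4.1 and 9.1.1, SAP 3.1) includes death, tamponade/perforation, pneumothorax, stroke, TIA and vascular access complications. SAP 3.1.3 names no subject class for the primary safety analysis, and SAP 4.1 refers only to eligible subjects. For the adverse event rates, SAP 3.4 says "all treatment and attempt subjects will be considered at risk for study related adverse events". SAP 5.6.1 sets the safety tipping-point cohort as all Treatment and Attempt subjects.

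**The concern.** Membership of the primary safety set depends on how far the procedure got, and that can depend on the harm being measured. If an access injury is mild and the operator continues, the subject becomes TREATMENT and the event counts. If the injury is severe enough to stop the case before a study catheter goes in, the event does not count. A harm that stops the case after a study device is in but before ablation makes the subject ATTEMPT, which is also outside the primary endpoint. Any error from this runs one way, towards a better event-free rate.

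At stake are the integrity of the safety estimate and the type I error of a test against an 85% performance goal. The two definitions of the set also mean that the tipping-point analysis would not be run on the population whose result it is meant to test.

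**Working it through.** **1. Where the subject goes on each reading.** Take a subject with a composite event after the procedure has begun but before any study device is inserted, whose case is then stopped.

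| Analysis | Read as INTENT | Read as ATTEMPT (second sentence) |
|---|---|---|
| Primary safety endpoint (Protocol 7.3) | out | out |
| Adverse event rates (SAP 3.4) | out | in |
| Safety tipping point (SAP 5.6.1) | out | in |
| Site reporting (Protocol 15.1) | reportable | reportable |
| Adverse event and death summaries in progress reports (SAP 5.1) | no set stated | no set stated |

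The first row is the same on both readings.

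**2. The plan's own figure.** Inputs from SAP 3.1.2: expected rate 90%, goal 85%, one-sided 5%, power 80%, attrition 7.5%. The smallest n above which exact binomial power stays at or above 80% is 304, and 304/(1 − 0.075) = 328.6, so 329. The stated size reproduces and this point does not change it. Enrolment of 415 leaves 415 − 329 = 86 subjects (20.7%) who may be non-TREATMENT. The documents do not say how many of those could be procedural harms.

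**3. Pass limit at n = 329, assuming no censoring.** With e events, S = 1 − e/n and the log-log limit is L = S^exp(1.645 × se), where se = √[e/(n(n − e))] / |ln S|.

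- e = 38: S = 0.8845, se = 0.01992/0.12273 = 0.1623, exponent 1.306, L = 85.19%. Pass.
- e = 39: S = 0.8815, se = 0.02022/0.12618 = 0.1602, exponent 1.302, L = 84.85%. Fail.

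**4. Chance of wrongly passing when the true rate is exactly 85%.** The number k of removed event subjects is an assumption. Expected events among 329 are 0.15 × 329 = 49.35. After removal, n₂ = 329 − k and p₂ = (49.35 − k)/n₂. The pass limit stays at 38 events for each n₂. The last column keeps p₂ but holds the analysed number at 329, because enrolment is meant to secure at least 329 TREATMENT subjects.

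| k | p₂ | P(≤ 38 events), n₂ = 329 − k | P(≤ 38 events), n = 329 |
|---|---|---|---|
| 0 | 0.1500 | 4.3% | 4.3% |
| 1 | 0.1474 | 5.9% | 5.7% |
| 2 | 0.1448 | 7.9% | 7.3% |
| 3 | 0.1422 | 10.4% | 9.3% |
| 4 | 0.1395 | 13.5% | about 11.8% |

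**5. Restoring omitted events in the planning case.** Start from 33 events in 329 (90.0%, L = 86.9%) and add k subjects, each with an event.

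| k | Events/n | Event-free rate | L | Result |
|---|---|---|---|---|
| 1 | 34/330 | 89.7% | 86.6% | pass |
| 3 | 36/332 | 89.2% | 86.0% | pass |
| 5 | 38/334 | 88.6% | 85.4% | pass |
| 6 | 39/335 | 88.4% | 85.12% | pass |
| 7 | 40/336 | 88.1% | 84.84% | fail |

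At the 38-event boundary a single restored event (39/330) moves L from 85.19% to 84.90% and reverses the result.

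**The case against.** A reader might infer that such a harm disappears from every safety analysis and that its outcome goes unrecorded. The documents do not support that. Adverse events are collected at baseline and index procedure (Protocol Table 5). Serious and procedure-related events are reportable whatever the class (15.1). Progress-report summaries state no population. Protocol 7.2 requires forms up to withdrawal and open events closed or documented as chronic. What is lost is a place in the endpoint and, on the INTENT reading, in the rates that have a defined population, together with any later study visit.

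A reader might also infer that INTENT is the only possible class. The second ATTEMPT sentence, read literally, captures the same subject. Protocol 7.3 also ties INTENT withdrawal to no ablation within 60 days of consent, and does not bar a second attempt in that window. The classification is ambiguous, but neither INTENT nor ATTEMPT brings the event into the primary test.

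A device-exposed set is a defensible choice for a device post-approval study. The statement in Protocol 17.1, "Since device and procedure relatedness do not affect the study endpoints", explains why no independent events committee is used; it does not define an analysis set, so it should not be read as settling this point. Still, the composite counts access and procedural harms whatever their cause, and a device-exposed result can be shown beside the fuller one.

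The remaining objections concern size, and they stand. The count of early-stopped cases is assumed, the documents do not describe anesthesia harms or when study catheters enter relative to transseptal access, and the planned case tolerates several omitted events.

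**Conclusion.** The point holds for the primary safety endpoint on either reading of Protocol 7.3, and for the adverse event rates and safety tipping point on the natural INTENT reading. Device insertion alone is not the boundary: for the primary endpoint the line is TREATMENT against the rest, so moving a subject from INTENT to ATTEMPT would not by itself change the result.

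The possible effect is material near the performance goal: a wrong-pass chance of 5.9% to 13.5% (5.7% to about 11.8% with 329 analysed) for 1 to 4 removed event subjects, against a stated 5%. It is small at the planned 90% rate, where 7 or more omitted events are needed to change the conclusion. These figures assume no censoring and an event in every removed subject. If no case stops this way, nothing changes. The documents therefore do not support a claim that the planned conclusion is unsafe. They do support defining the safety set once, so that membership does not depend on the severity of the harm.

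**What to change.** - **SAP 3.1.3, 3.4 and 5.6.1:** define one safety analysis set as every subject in whom the index procedure was begun (anesthesia or vascular access started), whatever the INTENT, ATTEMPT or TREATMENT class. Count primary safety events and reportable adverse events in that set. Censor subjects without an event at the end of their follow-up.
- **Protocol 7.3 and Table 11:** amend the INTENT and ATTEMPT sentences to match, including the one that keeps ATTEMPT out of the primary endpoint, which should no longer apply to safety. State which classification rule takes precedence where INTENT and the second ATTEMPT sentence overlap.
- **Follow-up:** reconcile the follow-up of subjects whose procedure was begun without a study device with the existing ATTEMPT safety follow-up.
- **Reporting:** list events before device insertion separately and give the device-exposed result as a supplementary analysis.

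The effectiveness set and the sample size are unchanged. The cost is a short SAP change and a matching protocol amendment, which goes to the ethics committees under Protocol 12.3. Event collection at the index procedure and the one-month ATTEMPT contact already exist. The downside is that the reported safety rate may be slightly less favourable and will include a few events before device exposure.

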#### 9.1.1.2. Sample Size

The sample size estimate was obtained using the normal approximation to the binomial distribution and verified through simulations based on Kaplan-Meier methodology. The following assumptions were used in the sample size calculation:

Assumptions	Primary Safety
Expected rate	90% 
Performance goal	85%
Attrition (per year)	7.5%
Significance level (one-sided)	5%
Power	80%

Under the hypothesis and assumptions outlined above, the required sample size for this endpoint is 329 TREATMENT subjects.

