4 GENERAL STATISTICAL METHOD

4.1 Analysis Sets

While each endpoint was individually powered, each endpoint analysis will use all available data from all eligible subjects, regardless of original calculated sample size.

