5.6 Sensitivity Analyses

5.6.1 Sensitivity analysis for the primary safety endpoint analysis

The sensitivity analysis -- tipping point analyses will be performed in order to characterize the impact of missing data on the main primary safety endpoint outcome by determining the point at which events in these subjects could have impacted the primary safety endpoint outcome. For the primary safety tipping point analysis, the overall cohort will consist of all Treatment and Attempt subjects. Tipping point analyses will be performed using the exact binomial distribution.

Tipping Point Analysis – Only subjects with complete data (subjects experienced the primary safety endpoint event or patients followed through 12 months) will be considered to have full follow-up data. All subjects with missing data (Subjects who withdraw before 12 months without experiencing an endpoint event will be classified as having missing data) will one by one be considered to have experienced an endpoint event. The rate and one-sided Clopper-Pearson lower 95% confidence bound will be calculated and lower confidence bound compared to the performance goal of 85%. The number of missing data subjects who would have needed to experience an event for the endpoint to be failed will be considered the tipping point for this analysis.

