5.6.2 Sensitivity analysis for the primary effectiveness endpoint analysis

The sensitivity analysis -- tipping point analyses will be performed in order to characterize the impact of missing data on the main primary effectiveness endpoint outcome by determining the point at which events in missing data subjects could have impacted the primary effectiveness outcome. For the primary effectiveness tipping point analysis, the overall cohort will consist of all Treatment subjects. The analysis will be performed using the exact binomial distribution.

Tipping Point Analysis- Only subjects with complete data (subjects experienced the primary effectiveness endpoint event or patients followed through 12 months) will be considered to have full follow-up data. Subjects with missing data (Subjects who withdraw or die before 12 months without experiencing an endpoint event will be classified as having missing data) will one by one be considered to have experienced an endpoint event. The rate and one-sided Clopper-Pearson lower 95% confidence bound will be calculated and lower confidence bound compared to the performance goal of

50%. The number of missing data subjects who would have needed to experience an event for the endpoint to be failed will be considered the tipping point for this analysis.

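### The primary safety cohort is not fixed: Protocol 7.3 as written leaves ATTEMPT subjects out, SAP 5.6.1 puts them in, and SAP 5.6.1 has no category for those who finish event-free at one month

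*Protocol*

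**What the plan says.** Protocol 7.3 defines an ATTEMPT subject as one who had a study device inserted but did not receive ablation per protocol, or who was not treated with both an open-irrigated catheter and the Rhythmia system. Of these subjects it says "Subjects will be followed for one month for safety reporting only" and "ATTEMPT subjects will count towards the enrollment ceiling and will not be used for analyses of the primary endpoint". It does not say which primary endpoint is meant; Protocol 9.1 and SAP 3 have two.

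On sizing, Protocol 9.1.1.2 (repeated in SAP 3.1.2) says "the required sample size for this endpoint is 329 TREATMENT subjects". On analysis sets, SAP 4.1 (same wording in Protocol 9.2.1) says only that "each endpoint analysis will use all available data from all eligible subjects, regardless of original calculated sample size". SAP 3.1.3, which describes the main Kaplan-Meier safety test, names no cohort and censors only subjects who withdraw.

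The sensitivity sections treat the two endpoints differently. SAP 5.6.1: "For the primary safety tipping point analysis, the overall cohort will consist of all Treatment and Attempt subjects". SAP 5.6.2: "For the primary effectiveness tipping point analysis, the overall cohort will consist of all Treatment subjects".

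SAP 5.6.1 then sorts subjects into two groups. Full follow-up data: "Only subjects with complete data (subjects experienced the primary safety endpoint event or patients followed through 12 months". Missing: "Subjects who withdraw before 12 months without experiencing an endpoint event will be classified as having missing data".

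**The concern.** The safety test is single-arm against a fixed 85% goal, so the choice of who is counted is part of the test. ATTEMPT status is decided after a study device is in the body. If 7.3 applies to safety, a tamponade or stroke before ablation can turn its own subject into an ATTEMPT and take the event out of the test. Such events would still appear in the tertiary adverse event rates (Protocol 9.1.4), but those carry no success criterion.

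The separate cohorts in SAP 5.6.1 and 5.6.2 suggest that ATTEMPT subjects may have been intended for safety and that the exclusion in 7.3 was meant for effectiveness. No text says so. If 7.3 does govern, SAP 5.6.1 tests the robustness of the main result in a different cohort from the one that produced it.

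The second gap follows from the one-month follow-up. An ATTEMPT subject with an event is complete. One who finishes the planned month without an event has not reached 12 months and has not withdrawn, so neither group fits. The main analysis has the same hole if ATTEMPT subjects are included, because SAP 3.1.3 gives no censoring rule for a planned early exit.

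**Working it through.** **Inputs from the documents.** Goal 85%, one-sided 5%, expected rate 90%, attrition 7.5% per year, 80% power, 329 TREATMENT subjects, 415 enrolled. The difference, 415 − 329 = 86, is the number of non-TREATMENT places, INTENT included. The INTENT/ATTEMPT split is not given.

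**Assumptions.** 10 or 17 ATTEMPT subjects (20 and 40 in step 5), with ATTEMPT event rates varied.

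**1. The plan's own figure.** An exact one-sample binomial test of 85% against 90% needs 304 subjects; 304/0.925 = 328.6, so 329. The stated size reproduces.

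**2. Effect on the chance of a false pass.** Fix the true event rate in all exposed subjects at 15%. With m ATTEMPT subjects at event rate r, the TREATMENT rate is q = [0.15 × (329 + m) − r × m]/329. For m = 17 and r = 0.30, q = (51.9 − 5.1)/329 = 0.1422. Without censoring, the log-log lower limit is p^exp[1.645 × se/(p|ln p|)], with se = √[p(1 − p)/n]. The smallest passing result is 291/329 (85.19%; 290/329 gives 84.85%). The chance of at least 291 event-free TREATMENT subjects is:

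| ATTEMPT event rate | m = 10 | m = 17 |
|---|---|---|
| 10% | 3.7% | 3.3% |
| 15% (equal) | 4.3% | 4.3% |
| 20% | 5.1% | 5.7% |
| 30% | 6.9% | 9.3% |

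Counting all exposed subjects (cut-offs 300/339 and 306/346), the test passes 3.8% to 4.0% of the time throughout.

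**3. Effect on an observed result.** At the planned rate, 296/329, the lower limit is 86.87%. Adding 10 ATTEMPT with 2 events (304/339) gives 86.60%; adding 17 with 3 events (310/346) gives 86.54%. Both pass. Reversal needs 7 events in 7 to 10 ATTEMPT subjects, or 8 in 17. With 25 TREATMENT withdrawals, 3 of the 33 TREATMENT events after day 30 and event-free ATTEMPT subjects censored at day 30, the Kaplan-Meier lower limits are 86.8% (TREATMENT only), 86.5% (10 with 2) and 86.4% (17 with 3). At the minimum pass, 291/329, adding 10 ATTEMPT with 2 events gives 299/339 and a limit of 84.97%, a fail.

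**4. Effect on the tipping point.** Take 33 TREATMENT events (about 10% of 329) and 25 withdrawals (about 7.5%). Turn withdrawals into events one by one until the one-sided Clopper-Pearson lower bound no longer exceeds 85%.

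| Cohort | Observed events | Tipping point |
|---|---|---|
| TREATMENT only, n = 329 | 33 | 6 |
| Plus 10 ATTEMPT with 1, 2 or 3 events, n = 339 | 34, 35, 36 | 6, 5, 4 |
| Plus 17 ATTEMPT with 1, 2 or 3 events, n = 346 | 34, 35, 36 | 7, 6, 5 |
| Event-free ATTEMPT dropped, 2 of 10, n = 331 | 35 | 4 |
| Event-free ATTEMPT dropped, 3 of 17, n = 332 | 36 | 3 |

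Calling event-free ATTEMPT subjects complete or missing makes no difference to the count: n and the observed events are the same, and fewer than 25 flips are needed. Only dropping them lowers it, and SAP 5.6.1 says the cohort is everyone in both groups.

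**5. Larger ATTEMPT groups.** In simulation with a true TREATMENT rate of 90%, 7.5% attrition and event-free ATTEMPT subjects censored at day 30, power is about 0.86 without ATTEMPT. With ATTEMPT event rates of 0%, 10%, 20% and 30% it is 0.93, 0.85, 0.77 and 0.64 for 20 ATTEMPT subjects, and 0.96, 0.87, 0.68 and 0.41 for 40.

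**The case against.** The best defence is that the cohort is settled. Protocol 7.3 excludes ATTEMPT subjects without exception, the safety sample size is in TREATMENT subjects, and SAP 2 describes the SAP as a supplement to the protocol. SAP 4.1 can then be read together with 7.3, and a sensitivity analysis may use a wider cohort. This is a fair reading, but it does not dispose of the point. SAP 5.6.1 is meant to test the main primary safety result, and it does so in subjects that 7.3 would exclude. The reading also leaves the safety cohort selected on something that happens after exposure.

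A second defence is size. At the planned 90%, no plausible mix of 10 or 17 ATTEMPT subjects reverses the result, a 20% ATTEMPT event rate moves the false-pass rate only to 5.1% or 5.7%, and the missing category has almost no numerical effect. All of that stands, and it limits the weight of the point.

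Third, Protocol 9.3.6 and SAP 6 require changes made before analysis to go into an amended, approved SAP, and later changes to be reported with reasons. That limits a late choice of cohort. It does not prevent one, since picking a reading of ambiguous text need not count as a change.

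Finally, adding ATTEMPT subjects brings in people seen for one month to an endpoint with 3-month and 12-month components, and counts events in subjects switched to non-study equipment. Both are real costs, and a clearly named TREATMENT-only cohort would also remove the inconsistency.

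**Conclusion.** The concern holds. Protocol 7.3, SAP 4.1 and SAP 5.6.1 do not fix one primary safety cohort, and SAP 5.6.1 gives no category to an event-free ATTEMPT subject who completes the planned month.

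The direction of any bias cannot be determined from the documents: TREATMENT-only is favourable only if ATTEMPT subjects have more events. Against the 4.3% baseline, the shift in false-pass probability for 10 / 17 ATTEMPT subjects is +0.7 / +1.3 points at a 20% ATTEMPT event rate, +2.5 / +4.9 at 30%, and −0.6 / −1.0 at 10%. The pass/fail result is at risk mainly near the goal, or if ATTEMPT subjects are numerous and their event rate is far from the TREATMENT rate. All ATTEMPT counts and rates here are assumptions. The missing category is a clarification with little numerical weight unless those subjects are dropped. The stated sample size is not in error.

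**What to change.** Preferred:

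- In Protocol 7.3 and 9.1.1 and SAP 3.1 and 4.1, define the primary safety set as every subject with any study device inserted (TREATMENT plus ATTEMPT).
- Limit the 7.3 exclusion to the effectiveness endpoints.
- Censor event-free ATTEMPT subjects at last contact, and keep TREATMENT-only as a supportive safety analysis.
- Use the same set in SAP 5.6.1, with event-free ATTEMPT subjects who finish at one month classified as missing and kept in the denominator.

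Alternative, if the sponsor wants TREATMENT-only as primary: have 7.3 and SAP 4.1 say so for safety by name, run the SAP 5.6.1 tipping point on that cohort, and show Treatment plus Attempt as a separate sensitivity analysis.

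Under either choice, align the TREATMENT definition: the synopsis requires treatment to be completed successfully, while 7.3 and Table 11 require only that it be undergone.

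The cost is wording. The 329 can stay as a minimum number of TREATMENT subjects, and ATTEMPT safety data are already collected for one month. That month covers the seven-day acute window, but not the full 3-month window (fistula, effusion) or 12-month window (pulmonary vein stenosis), so censored ATTEMPT subjects add nothing after it. The reported safety rate may be slightly less favourable, and events in subjects switched to non-study equipment would count; the supportive TREATMENT-only analysis would show both.
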